December 10, 2025

RESEARCH PROTOCOL FOR THE PROJECT

FOSTERING UKRAINE'S CAPACITY IN DELIVERY AND RESEARCH OF INNOVATIVE EVIDENCE-BASED PTSD TREATMENT

SECTION 1: PROJECT

Title:	Fostering Ukraine's capacity in delivery and research of innovative evidence-based PTSD treatment
Acronym:	Lux4UA

Applicant(s):

Researcher/Student	Name:	[name]
	Position at UL:	Research scientist
	Faculty / IC:	FHSE
	Research Unit:	Department of Behavioural and Cognitive Sciences
	Telephone no:	([contact]
	Email:	[contact]

Principal Investigator	Name:	[name]
	Position at UL:	Research scientist
	Faculty / IC:	FHSE
	Research Unit:	Department of Behavioural and Cognitive Sciences
	Telephone no:	([contact]
	Email:	[contact]

Funding:

Source:	FNR under LUXAID BRIDGES CALL
---------	--------------------------------------

SECTION 2: SHORT SUMMARY OF THE PROJECT

(including research design and methodology)

The Lux4UA Project's goal is to foster Ukrainian mental health professionals' capacity in transdisciplinary research on innovative, evidence-based trauma treatment (Reconsolidation of Traumatic Memories (RTM) Protocol) in humanitarian emergencies due to war and displacement. To accomplish this goal, the RTM Protocol Effectiveness and Feasibility studies will be conducted.

The RTM Protocol effectiveness study implies a randomised field trial comparing RTM with treatment-as-usual (Trauma-Focused Cognitive Behavioral Therapy (TF-CBT), Eye Movement Desensitization and Reprocessing (EMDR), or pharmacotherapy) across three customary clinical settings in Ukraine (hospital in-patient, hospital out-patient, private psychotherapy). The primary outcome is the loss of Post-Traumatic Stress Disorder (PTSD) diagnosis or change in symptoms; secondary outcomes include depression and anxiety at post-treatment, 6 m and 12 m follow-up.

Objective 1: *To compare the effectiveness of the RTM Protocol for the treatment of trauma-related mental conditions with other evidenced-based trauma-focused therapies (TF-CBT, EMDR and medication).*

Objective 2: *To investigate the effectiveness of the RTM Protocol for the treatment of trauma-related mental conditions in different settings of mental health (MH) care (inpatient and outpatient hospital care for veterans and private psychotherapy for civilians)*

The RTM Protocol and Training feasibility study will evaluate the RTM Protocol's acceptability and adaptability during training and practice through case statistics, satisfaction surveying of MH practitioners and clients, and focus-group interviews with MH practitioners.

Objective 1: *To analyse the acceptability of the RTM Protocol among MH professionals and persons with trauma-related MH conditions)*

Objective 2: *To analyse the adaptability (Usability of the Ukrainian language versions) of the RTM Protocol*

Data will be collected, pseudonymised in Ukraine by implementing partners - the Centre of Mental Health and Rehabilitation "Forest Glade" of the Ministry of Health of Ukraine (RCFG) and the National Psychological Association of Ukraine (NPAU), and transferred in fully anonymised, aggregated form to the University of Luxembourg for analysis. Findings will inform humanitarian response policy and sustainable capacity-building for evidence-based PTSD treatment in low-resource, conflict settings.

SECTION 3: AIM OF EACH OF THE STUDIES

Study No.	Aim	Study will involve: Please tick all appropriate boxes
Study 1: The RTM Protocol effectiveness study	To compare the effectiveness of the RTM Protocol for the treatment of PTSD with other evidenced-based trauma-focused therapies (TF-CBT, EMDR and medication) in different settings of MH care accustomed for Ukraine (inpatient and outpatient hospital care for war veterans and psychotherapy for civil trauma survivors).	 Human participants  Vulnerable population  Human biological material  Pre-collected biological material  Personal data  Pre-collected personal data  risks on the environment  risks on the society
Study 2: The RTM Protocol and Training feasibility study	To analyse the acceptability of the RTM Protocol among MH professionals and persons with PTSD and the adaptability of the RTM Protocol & RTM Training for the country context.	 Human participants  Vulnerable population  Human biological material  Pre-collected biological material  Personal data  Pre-collected personal data  risks on the environment  risks on the society

Please expand the rows in case of additional studies.

SECTION 4: DETAILS OF EACH STUDY

Study 1: The RTM Protocol Effectiveness Study

Target sample size: (Please justify the target sample size, either statistically or by referring to existing literature)	
The research sample for the EFFECTIVENESS STUDY is expected to be 120 participants (people with PTSD), approximately equally distributed between experimental and control groups (at least 20 participants).
 
The sample expectancy is based on case numbers estimated by every MH care provider involved in the Project. The allocation ratio was calculated based on the assumption that the mean of PCL-5 would be 25.0 for the control group and 21.0 for the experimental group (SD of 3.0); a type 1 risk is 5.0%, and a type 2 risk is 20.0%, for the bilateral test and a dropout rate at 20.0%, the minimum N of participants in each group should be equal to 12.

Key inclusion criteria:	Key inclusion criteria for the effectiveness study participants are (1) being adults \geq 18 years, (2) having a diagnosis of PTSD determined by DSM-5-TR or ICD-11 and/or (3) having PTSD symptoms causing clinically significant distress or impact on social, occupational, or other areas of functioning defining on base of using PTSD Checklist PCL-5, (4) being resident of Ukraine.
Key exclusion criteria:	Key exclusion criteria for the effectiveness study participants are (1) having any other acute comorbid mental health conditions, (2) receiving any other parallel PTSD treatment, (3) being unable to provide informed consent, has severe cognitive impairment, or is otherwise unlikely to adhere to study procedures.
Age range of participants:	Adults aged 18-65.
Country/ies of recruitment:	Ukraine
Expected duration of procedure:	Data collection will occur at baseline (diagnostic session), 1 month after complete treatment application, in 6 months (follow-up booster session), and in 12 months (second follow-up booster session) and will take approximately 15 min each, 45 min per person.
Data Collection:	
Paper questionnaires, digital entry; no audio/video.
 
Data on age, gender, veteran and IDP statuses, residency, type of trauma, medical diagnosis and symptoms, scores from PCL-5 (for PTSD), PHQ-9 (for depression), GAD-7 (for anxiety) diagnostic scales will be collected from printed questionnaire sheets filled in by participants.
 
PTSD diagnosis will be collected from medical records.
 
Names, email-address, phone number will be collected from printed informed consent.
 
Data transfer. Aggregated, fully anonymised raw data will be shared by implementing partners' coordinators through Zenodo under closed access and using the EUSurvey Platform (an online survey-management

	
system developed by the European Commission) only with PI [name].

Methodology:	
Research design. The RTM Protocol effectiveness study implies a randomised field trial comparing RTM with treatment-as-usual (TF-CBT, EMDR or pharmacotherapy). It is chosen and will be standardised based on CONSORT 2010 Statement: reporting parallel group randomised trials. To enhance the external validity of the findings, all the interventions are planned to be explored among three different settings of mental health care accustomed to Ukraine: mental health hospital care (inpatient and outpatient care for veterans) and psychotherapeutic practice (for civil trauma survivors).
 
Measures. Primary outcome effectiveness measures are MH professional proved existence or loss of PTSD diagnosis and/or PTSD symptoms severity measured by PTSD Checklist PCL-5 (re-experiencing of trauma, avoidance of trauma-related stimulus, negative alterations in cognition and mood, hyper-arousal).
 
Among secondary outcome measures will be the existence and severity of depression and anxiety-related symptoms according to PHQ-9 and GAD-7 scales.
 
Data analysis. Descriptive Statistics: means, SDs, medians, frequencies and percentages, baseline comparability between groups (t-tests, chi-square tests). Primary and Secondary Outcome Analysis: mixed-effects repeated measures ANOVA. Handling Missing Data: multiple imputation or maximum likelihood estimation under MAR assumption. Effect Size Reporting: Cohen's d, odds ratios, and 95% confidence intervals.
 
Data collection will be in Ukrainian language (all the scales are validated in Ukrainian and recommended by the World Health Organisation for the screening of the mentioned mental health conditions) at baseline (diagnostic session), 1 month after complete treatment application, in 6 months (follow-up booster session), and in 12 months (second follow-up booster session).

Study 2: The RTM Protocol and Training Feasibility Study

Target sample size: (Please justify the target sample size, either statistically or by referring to existing literature)	
The research sample for the FEASIBILITY STUDY is expected to be 20 participants according to the trauma-related cases/workforce availability ratio of implementing partners: 10 persons from each site.
 
The number of clients is expected to be 60 persons (persons treated with the RTM Protocol) according to the RTM Protocol effectiveness study description.

Key inclusion criteria:	
Key inclusion criteria for MH professionals are (1) holding an accomplished higher education degree in the mental health area (psychology, psychiatry, psychiatric nursing, clinical social work), (2) having at least three years of hands-on clinical experience in mental-health settings, (3) being formally trained to deliver mental health care

	
to people exposed to trauma through accredited coursework, supervised practice, or equivalent, (4) meeting Ukrainian licensing and registration requirements mandated by health-care regulations and the implementing organisation's internal policies, (5) committing to attend the full training, complete all associated supervision sessions, and deliver the Protocol as specified by the study timeline.
 
The client sample is the same as for the study 1.

Key exclusion criteria:	
Key exclusion criteria for MH professionals are (1) being under investigation, suspension, or other disciplinary action by a professional body or employer, (2) lacking mandatory professional continuing education for the last year (min 40 hours), (3) having caseload exceeding the threshold for service quality requirements (> 30 active therapy clients).
 
The client sample is the same as for the study 1.

Age range of participants:	
Adults aged 18-65 (with regard to the eligibility criteria).
 
The same sample as for the study 1.

Country/ies of recruitment:	
Ukraine

Expected duration of procedure:	
MH Professional will be engaged into case statistic collection (30 min per case, 1 hour per person); satisfaction surveying (15 min per person) and focus-group interviews (1,5 hour of group work).
 
Clients will be engaged into satisfaction surveying (15 min per person).

Data Collection:	
Intervention Usability Scale, satisfaction survey; audio-recorded focus-groups interviews.
 
Data on MH professionals' occupation, place of work, professional experience, trauma-centred methods used; data from Intervention Usability Scale and case statistics (number of trauma-related requests, trauma-specific cases treated with the RTM, hours spent for each case treatment, process comfort, expected and reached results, usefulness for different types of trauma and trauma-related symptoms), will be collected from printed questionnaire sheets filled in by participants.
 
Data on MH professionals' Protocol use features, implementation benefits and challenges, effects and consequences, clients' acceptance and perception will be collected and audio-recorded during focus-group interviews.
 
MH professionals' names, email-address, phone number will be collected from printed informed consent.
 
Data on clients' treatment satisfaction (process comfort, expected and reached results, usefulness for client's types of trauma and trauma-related symptoms) will be collected from printed questionnaire sheets filled in by participants.

	
Clients' names, email-address, phone number will be collected from printed informed consent.
 
Data transfer. Aggregated, fully anonymised raw data will be shared by implementing partners' coordinators through Zenodo under closed access and using the EUSurvey Platform (an online survey-management system developed by the European Commission) only with PI [name].

Methodology:	
Research design. The RTM Protocol and Training feasibility study will evaluate the RTM Protocol acceptability and adaptability during training and practice through case statistics, satisfaction surveying of MH practitioners and clients, and focus-group interviews with MH practitioners. As a standardisation base for the feasibility study the Framework for the development and evaluation of complex interventions issued by the National Institute for Health and Care Research (NIHR) was chosen.
 
Measures. To assess the RTM Protocol's acceptability by MH professionals, case statistics such as the number of trauma-related requests, trauma-specific cases treated with the RTM, hours spent for each case treatment, etc., will be collected. The standardised Intervention Usability Scale will also be applied.
 
Also, satisfaction with the procedure and therapeutic process from both sides (clients and MH professionals) will be surveyed regarding process comfort, expected and reached results, usefulness for different types of trauma and trauma-related symptoms, etc.
 
MH professionals' feedback will also be considered during the focus-group analysis. The focus-group protocol and script will be developed with input from every implementing partner to match the local frame of mental health care. The script previews topics such as the RTM Protocol use features, the RTM Protocol implementation benefits and challenges, the RTM Protocol effects and consequences, the RTM Protocol clients' acceptance and perception, etc.
 
The RTM Protocol's adaptability will be measured by analysing the case statistics and MH professionals' feedback for the Ukrainian version of the protocol.
 
Data analysis. For Quantitative Analysis will be utilised descriptive statistics (frequencies, means, SDs for usability and satisfaction scores), correlation analysis (between usability scores and satisfaction or case outcomes (e.g., Spearman's rho)).
 
Qualitative Analysis will be conducted using thematic analysis (transcripts coded using inductive and deductive approaches, themes mapped to NIHR framework domains), charting and mapping.

SECTION 5: RISK ASSESSMENT AND RISK MINIMIZATION

Study 1: The RTM Protocol Effectiveness Study

Potential risk(s)	Extent of risk(s) and measures taken

Human participants are involved in the study with potential risk related to
 
 Physical harm  Psychological harm  Invasion of privacy  Social and economic harm  Other
	
Personal data will be collected (see data collection section).
 
Data collection measures. Implementing partners' coordinators will collect data using printed versions of questionnaires (which will be destroyed after data e-input and prior this time they will be stored in a secure storage cabinet). Mental health professionals involved in the research will collect data on clients (people with PTSD) using clinical scales which will be destroyed after data e-input and before it will be stored in a secure storage cabinet.
 
Data Storage measures. The e-data will be stored on encrypted hard drives and will be accessible only to implementing partners' coordinators. They will create password-protected access to the data with the help of the organisations' IT departments.
 
Data Pseudonymization measures. The data will be pseudonymized by the implementing partners' coordinators and professionals involved in the research for the purpose of follow-up assessments using European Data Protection Board Guidelines on Pseudonymisation, 2025.
 
Usage and storage of personal data will fully comply with Ukrainian legislation, the Civil Code of Ukraine, and the Law of Ukraine on the Protection of Personal Data.
 
No mentioned non-anonymized personal data will be used for the research purposes, transferred or processed in Luxembourg.


Are there any specific risks to the human participants involved, if any.
	
Risk of adverse effects is usually considered in studies on mental health interventions. It is important to mention that possible adverse effects are minimised by the RTM Protocol procedure itself, which is focused on processing traumatic events without triggering emotional hyperarousal by quick termination of every therapeutic technique at first sign of client' distress.
 
Nevertheless, clients' support will be organised according to existing procedures and requirements of mental health care established by the implementing partners (RCFG, NPA) and through adverse-effect management and reporting that aligns with safety requirements of the CONSORT-Harms 2022 framework.
 
Adverse-effect management includes the following measures:
 
 - anticipating adverse effects (PTSD symptoms deterioration; emotional distress); - adverse effects monitoring & detection (using implemented into the Protocol assessments procedures as measurement of subjective distress and physiological arousal calibration, as

	
well as additional monitoring with the PCL-5 (for PTSD), PHQ-9 (for depression), and GAD-7 (for anxiety) diagnostic scales;
 
- mitigating adverse effects (terminating the intervention, utilizing grounding and "break state" techniques, referring for other types of help and support, providing extra visits, crisis referrals, and medication);
 
- recording every episode of adverse effects in patient documentation;
 
- reporting adverse effects to the site coordinator for processing and reflection in study reports and publications.
 
No mentioned project activities will be executed in Luxembourg or with Luxembourg or EU residents.

--	--

Study 2: The RTM Protocol and Training Feasibility Study


Human participants are involved in the study with potential risk related to
 
 Physical harm
 
 Psychological harm
 
 Invasion of privacy
 
 Social and economic harm
 
 Other
	
Personal data will be collected (see data collection section).
 
Data collection measures. Implementing partners' coordinators will collect data using printed versions of questionnaires (which will be destroyed after data e-input and prior this time they will be stored in a secure storage cabinet) and focus-group interviews audio-recordings with following transcription. Mental health professionals involved in the research will collect data on clients (people with PTSD) using printed versions questionnaires which will be destroyed after data e-input and before it will be stored in a secure storage cabinet.
 
Data Storage measures. The e-data will be stored on encrypted hard drives and will be accessible only to implementing partners' coordinators. They will create password-protected access to the data with the help of the organisations' IT departments.
 
Data Pseudonymization measures. The data will be anonymized by the implementing partners' coordinators.
 
Usage and storage of personal data will fully comply with Ukrainian legislation, the Civil Code of Ukraine, and the Law of Ukraine on the Protection of Personal Data.
 
No mentioned non-anonymized personal data will be used for the research purposes, transferred or processed in Luxembourg.

Are there any specific risks to the human participants involved, if any.
	
There are no anticipated specific risks for the human participants.

SECTION 6: DATA PROTECTION

Study 1: The RTM Protocol Effectiveness Study

The Project PI will have access only to aggregated, anonymised data. The implementing partners' coordinators and professionals involved in the research will collect, pseudonymise (for the purpose of follow-up assessment in two weeks, six months, and one year), and anonymise the clients' data. Implementing partners' coordinators will aggregate the data and input it on the EU Survey Platform (an online survey-management system developed by the European Commission) to transfer it to Luxembourg. The transferred data will be stored on the University of Luxembourg-protected server ATLAS for up to 10 years.

Pseudonymisation and Coding Strategy will be based on the European Data Protection Board (EDPB) Guidelines on Pseudonymisation, 2025.

The study design requires pseudonymisation only for follow-up post-treatment assessments for PTSD symptoms severity (PCL-5), existence and severity of depression (PHQ-9), and anxiety-related (GAD-7) symptoms at 2 weeks, 6 months, and 12 months post-treatment. The main purpose is to enable linkage of repeated assessments while restricting direct identification.

It is planned to have 3 experimental groups in 3 different treatment settings (Hospital Inpatient, Hospital Outpatient, Psychotherapeutic Practice) and 3 control groups with "treatment-as-usual" in the same three types of settings, with 20 participants each. It creates 6 study samples with 120 participants in total. Each participant will receive a unique study participant ID (PID) upon inclusion, generated as: [GroupCode]- [SettingCode]- [SequentialNumber]. For example, ExpHIP001: Experimental group, Hospital Inpatient setting, Participant 1.

Enrolment and randomisation (steps taken at baseline and immediately after each enrolment). As soon as a participant is enrolled, the site coordinator assigns a sequential number, allocates the study sample using Randomisation Software, and creates a PID. The coordinator writes down the PID on each paper document for follow-up contact and records the PID on the pseudonymization key list uploaded to the NPA/ RCFG staff laptop/desktop (encrypted hard drives).

Data collection (before and during follow-up assessments). Whenever data are gathered later, the research staff involved (therapists, assessors, or other professionals) manually write each participant's PID on every paper document related to that follow-up contact, allowing the data to be linked back to the correct person without revealing their identity.

For the follow-up post-treatment assessments (2 weeks / 6 months / 12 months), sites' coordinators will use the secure key to retrieve participant contact from the PID. Re-assessment tools will be administered with the same PID. Results will be stored again using a pseudonym only.

Study 2: The RTM Protocol and Training Feasibility Study

The Project PI will have access only to aggregated anonymised data (professionals-participants' occupation, place of work, duration of professional experience, trauma-centred methods used, data from satisfaction surveying, Intervention Usability Scale and focus-group interview etc.) Implementing partners' coordinators will collect, anonymise, aggregate the data and input it on the EUSurvey Platform (an online survey-management system developed by the European Commission) to transfer it to Luxembourg. Focus-group interview transcripts' transfer to Luxembourg will be done through Zenodo under closed access. The transferred data will be stored on the University of Luxembourg-protected server ATLAS for up to 10 years.

Comments on the possible misuse of the research:

The Lux4UA project is designed exclusively to evaluate the effectiveness and feasibility of the RTM Protocol. It does not aim to collect prevalence data, epidemiological statistics, or any form of population-level surveillance. All data are collected solely for the purpose of assessing therapeutic outcomes and implementation feasibility within predefined clinical settings.

No new diagnostic tools are being developed, and no data will be used to infer broader mental health trends or conditions across populations. The study samples are limited, purposive, and context-specific, selected based on clinical availability. Therefore, the findings cannot be extrapolated to estimate prevalence or inform policy beyond the scope of treatment evaluation.

Furthermore, the project does not involve any form of geolocation, behavioral tracking, or longitudinal profiling beyond anonymized follow-up assessments. All data are pseudonymized and aggregated before analysis, and no individual-level identifiers are retained or transferred.

Given the sensitive context of war and displacement, we acknowledge the theoretical risk of misinterpretation or misuse of mental health data. To mitigate this, the project adheres strictly to ethical guidelines from EFPA, CIOMS, and the IASC, and all implementing partners operate under national ethical oversight. The research outputs will be framed explicitly within humanitarian and clinical care contexts, avoiding any language or framing that could be construed as diagnostic surveillance or military profiling.

We also commit to transparency in dissemination: all publications will include clear disclaimers about the scope and limitations of the data, and no data will be shared with third parties outside the research consortium.

Data storage

	Raw data (incl. video or audio recordings)	Processed data (anonymized, pseudonymized)	Document(s) containing the names, contact information and personal details (the pseudonymisation key list)	Other material
Data carrier (digitalized or paper form)	Paper questionnaires Focus-group interview audio-recordings.	Excel files with fully anonymised data exported from EUSurvey Platform Word files with fully anonymised data transcribed from focus-group interview audio-recordings.	Informed consent forms, pseudonymization key list.	
Number of copies	Paper questionnaires for each client, 120 copies; for each MH professional, 40 copies. Focus-group interview audio-recordings, 1 copy for each implementing partner.	Numbers required by the needs of analysis, 1 copy for each type of data.	Informed consent forms for each client, 120 copies; for each MH professional, 40 copies. Pseudonymization key list, 1 copy for each site.	
Storage Location	Paper questionnaires are stored in locked cabinets at the sites' locations in Ukraine. Focus-group interview audio-recordings are stored locally on encrypted hard drives of implementing partners.	EUSurvey Platform (for data collection); ATLAS server (for data analysis and storage); Repository Zenodo (under closed access for data transferring; under open-access repository for open-access publications); Repository ORBilu (for open-access publications)	Informed consent forms are stored in locked cabinets at the sites' locations. Pseudonymization key lists are stored locally on encrypted hard drives of implementing partners.	
Retention period	Paper questionnaires will be destroyed after digital entry.	on EUSurvey Platform for 1 year; on ATLAS for up to 10 years; on Zenodo for the repository's lifetime, on ORBilu for the repository's lifetime.	Identifying data will be deleted 5 years following end of research project.	

Data access

Data collection. *Implementing partners' coordinators ([name] from the RCFG, [name] from the NPA) will collect data on MH professionals using printed versions of questionnaires and focus-group interviews audio-recordings with the following transcription. All the data will be destroyed after data digital entry (made by coordinators) and prior to this time they will be stored in a secure storage cabinet and on encrypted hard drives.*

Mental health professionals involved in the research will collect data on clients (people with PTSD) using printed versions of questionnaires and clinical scales, which will be destroyed after data digital entry (made by coordinators) and prior to this time they will be stored in a secure storage cabinet.

Data Storage. *The e-data will be stored on encrypted hard drives and will be accessible only to implementing partners' coordinators. They will create password-protected access to the data with the help of the organisations' IT departments.*

Data Pseudonymization. *The implementing partners' coordinators ([name] from the RCFG, [name] from the NPA) will pseudonymize the data for follow-up assessments.*

Data sharing. *Aggregated, fully anonymised raw data will be shared by implementing partners' coordinators ([name] from the RCFG, [name] from the NPA) through Zenodo under closed access and using the EUSurvey Platform (an online survey-management system developed by the European Commission) only with PI [name].*

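### Outcome assessments are timed from a treatment completion that is defined for no arm, so participants without a completion date have no assessment date

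*Protocol*

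**What the plan says.** - **Section 4, Study 1, Expected duration of procedure and Methodology.** After baseline, data are collected "1 month after complete treatment application, in 6 months (follow-up booster session), and in 12 months (second follow-up booster session". Completion of treatment is the origin of the first of these assessments only ("1 month after complete treatment application"). No origin is given for the other two.
- **Section 6, Study 1.** The pseudonymisation strategy places the same scales "at 2 weeks, 6 months, and 12 months post-treatment". Here all three follow-ups run from the end of treatment, and the first is at 2 weeks, not 1 month. The opening paragraph of that section also gives two weeks.
- **Section 4, Study 1, Methodology.** The design is a trial "comparing RTM with treatment-as-usual (TF-CBT, EMDR or pharmacotherapy". No course length is given for RTM or for any of the three control treatments, and none has a stated end point.
- **Section 5, Study 1.** The measures for handling adverse effects include "mitigating adverse effects (terminating the intervention" and referral elsewhere.
- **Section 6, Study 1, on enrolment.** "As soon as a participant is enrolled, the site coordinator assigns a sequential number, allocates the study sample using Randomisation Software". A randomisation date therefore exists for everyone.
- **Section 4, Study 1, analysis.** The outcome analysis is a "mixed-effects repeated measures ANOVA", with missing data handled by "multiple imputation or maximum likelihood estimation under MAR assumption".

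**The concern.** Completion of treatment happens after randomisation and depends on what was received and how it went. Timing from end of treatment can work when both arms have defined courses and there is a rule for people who do not finish. The protocol has neither.

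Two consequences follow. First, the rule gives no date to a participant whose treatment has no defined end or was stopped early. Site staff would have to improvise a date or leave the assessment out. Stopping because symptoms worsened is related to outcome, so assessments lost in this way would not be a random subset. Second, any difference in course length between arms becomes a difference in time since randomisation at what the analysis treats as the same visit. Recovery over time and outside events in a country at war could then enter the comparison of RTM with usual treatment.

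**Working it through.** **1. The protocol's own figure.** The inputs, from Section 4 (Target sample size), are PCL-5 means of 25.0 and 21.0, SD 3.0, two-sided 5% type 1 risk, 20% type 2 risk and 20% dropout.

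n per group = 2 × (1.960 + 0.842)² × 3.0² / 4.0² = 8.83, rounded up to 9. With dropout, 9 / (1 − 0.20) = 11.25, rounded up to 12.

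This reproduces the stated minimum of 12. The t-test version gives 10, then 10 / 0.80 = 12.5, rounded up to 13. The sample size is not affected by this point. It matters here only as the source of the 20%.

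**2. Does every randomised participant get a date?**

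| Situation | Completion date defined? | Assessment date under the rule |
|---|---|---|
| Finishes a psychotherapy course (RTM, TF-CBT, EMDR) | Not defined; a site could infer one | 1 month later (Section 4) or 2 weeks later (Section 6) |
| Pharmacotherapy | No end point stated | None that can be derived |
| Intervention terminated early | Never completed | None that can be derived |

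No section supplies a fallback date, and none dates a post-baseline assessment from enrolment or randomisation.

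**3. How many could be affected?** 0.20 × 120 = 24 in total. That is 12 of 60 per arm, or 4 of 20 in each of the six samples. The protocol does not divide dropout into stopping treatment and loss to follow-up. People lost to follow-up are unmeasured under any timing rule, so 24 is a ceiling for the dropouts.

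**4. Elapsed time since start (course lengths assumed, as the protocol gives none).** One month is taken as 4.3 weeks.

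| Assumed course (weeks) | First assessment at 1 month (weeks from start) | First assessment at 2 weeks (weeks from start) |
|---|---|---|
| 2 | 6.3 | 4 |
| 4 | 8.3 | 6 |
| 8 | 12.3 | 10 |
| 12 | 16.3 | 14 |
| 16 | 20.3 | 18 |

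A difference in course length passes one-for-one into assessment time. For example, 4 against 12 weeks gives 8.3 against 16.3, a gap of 8 weeks.

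**5. Can this be turned into PCL-5 points?** Shift = gap in weeks × drift per week. With an assumed gap of 4 to 12 weeks and an assumed drift of 0.1 to 0.5 points a week, the shift runs from 4 × 0.1 = 0.4 to 12 × 0.5 = 6.0 points. Against the planned 4-point difference that is 10% to 150%. Both inputs are invented, and early drift need not persist to 6 or 12 months. The width of the range shows that the protocol does not determine the size. It is not an estimate.

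**6. Does the missing-data plan repair it?** Imputation or likelihood estimation under MAR addresses values missing at a scheduled visit. It does not supply a date for a visit the rule never scheduled, and the MAR assumption is strained if stopping follows worsening symptoms.

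**The case against.** A rule worded identically for both arms in a pragmatic field trial is not wrong in itself. Equal time since end of treatment and equal time since randomisation answer different questions, and the choice between them is partly one of preference. That stands, which is why re-dating every visit is offered below as a preference and only the fallback date as a need.

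Several stronger readings are tempting and go further than the protocol:

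- *Medication is ongoing and course lengths differ, so the arms are measured at different times.* This is an inference from the mix of comparators. The protocol gives no durations.
- *Every follow-up is anchored to completion.* Section 6 says so. Section 4 ties only the first assessment to completion.
- *The trial becomes a comparison of completers.* No section restricts follow-up or analysis to completers. Participant IDs are assigned at enrolment, and coordinators retrieve contact details from them with no completion condition. Losing the non-completers is a risk of following the rule literally, not a stated intention.
- *The bias can be quantified.* One could assume 10% stopping on RTM, 30% on usual treatment, and stoppers 10 points worse, giving 0.30 × 10 − 0.10 × 10 = 2.0 points. But a 30% subgroup scoring 10 points worse alone implies an SD of 10 × √(0.3 × 0.7) = 4.6, which contradicts the planned SD of 3.0. The sum also ignores the planned MI or ML. It should not be used.

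It can also be said that the handling of non-completers belongs in an analysis plan, which is not at hand. For the analysis, that is fair. But the visit schedule is stated in the protocol, sites book from it, and a later analysis plan cannot recover assessments that were never made.

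**Conclusion.** The point holds in a limited form. Completion is undefined for every arm, and the rule as written gives no assessment date to participants who have no completion date. That follows from the text without any assumption about course lengths. Up to about 24 of 120 participants could be affected, if all of the assumed 20% dropout were early stopping. Any control participants on medication without an end point would be a separate group, whose number the protocol does not allow to be estimated.

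Unequal timing between arms is conditional on unequal course lengths, and neither it nor any resulting bias can be sized from the protocol. The conflict between 1 month in Section 4 and 2 weeks in Section 6 is a plain contradiction. This review does not say which timing is right. Overall this is a cheap improvement worth making; it does not show that the comparison is invalid.

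**What to change.** In Section 4, Study 1:

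1. State that every randomised participant is assessed at each time point, whether or not treatment was completed.
2. Set a fixed assessment date counted from randomisation, the same in both arms, at least for anyone with no completion date and preferably for all outcome assessments.
3. If an end-of-treatment anchor is kept for those who finish, define for assessment purposes when each treatment counts as complete.
4. Record days since randomisation at each assessment.
5. Reconcile the 1-month timing with the 2-week timing in Section 6, and state the origin of the 6- and 12-month assessments.

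The cost is protocol wording and some rescheduling. Randomisation dates exist and coordinators already hold contact details, so no new system is needed. The downside is real, though. The 6- and 12-month assessments are tied to booster sessions, and dating them from randomisation may separate the two, which could mean additional contacts. Some assessments would also fall at a different interval after the end of treatment, and without known course lengths a fixed date could fall before treatment ends. The dates should therefore be chosen with the expected course lengths in view.
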